#### **11.3.3.2 Laboratory Data**

Laboratory data (hematology, blood chemistry, and urinalysis parameters) will be presented for each treatment group using descriptive statistics, including mean and mean change from baseline values at each scheduled time point. Shift tables will display numbers of subjects with normal/abnormal values at baseline versus post-treatment. The frequency of laboratory abnormalities will be tabulated. By-subject data listings will flag laboratory values that are outside normal reference ranges or markedly abnormal findings.

#### **11.3.3.3 Vital Signs**

Descriptive statistics for observed values and change from baseline in vital sign parameters [blood pressure (systolic and diastolic), body temperature, pulse, and respiratory rate] will be presented by visit and treatment group.

#### **11.3.3.4 Electrocardiograms**

Descriptive statistics for observed values and change from baseline in (continuous) ECG parameters (e.g., RR, PR, QTc) will be presented by visit and treatment group. Shift tables in relation to overall interpretation (Normal, Abnormal Not Clinically Significant [NCS] and Abnormal Clinically Significant [CS]) from baseline to each post-baseline visit will be presented.

#### **11.3.3.5 Other Safety Assessments**

The C-SSRS will be summarized at each visit by treatment using descriptive statistics.

Abnormal physical examinations and MRI results will be summarized descriptively by visit and treatment group.

### **11.3.4 Demographic and Baseline Characteristics**

Treatment groups will be compared with respect to subject demographics, and baseline characteristics will be summarized using descriptive statistics. No formal statistical analysis tests will be performed.

### 11.3.5 Interim Analysis

The purpose of the interim analysis is to determine if COR388 HCl is efficacious and conduct a sample size re-estimation. One unblinded interim analysis will be performed after approximately 300 subjects have completed 24 weeks of treatment. The DMC will review unblinded data for the mean change from baseline in ADAS-Cog 11 and the mean change from baseline in the CDR-SB post 24 weeks of treatment. Both treatment comparisons will be assessed at the interim analysis: 40 mg COR388 HCl and 80 mg COR388 HCl vs. placebo for the two co-primary endpoints (i.e., mean change from baseline in ADAS-Cog 11 and mean change from baseline in CDR-SB at Week 24). Analyses will be performed as specified in the approved final study SAP.

The DMC should return to the Sponsor one of four recommendations as follows:

1. Stop the study early for overwhelming efficacy defined as  $p < 0.005$  adjusted for multiplicity using the [Benjamini-Hochberg](#) procedure for both ADAS-Cog 11 and CDR-SB in favor of either 40 mg COR388 or 80 mg COR388 HCl over placebo;
2. Stop either or both arms (stopping both arms would mean stopping the study) early for futility defined as  $p < 0.05$  on either ADAS-Cog 11 or CDR-SB in favor of placebo over active dose(s), and the other endpoint for the same dose is directionally favoring placebo;
3. Continue with no sample size adjustment; or
4. Continue with an appropriate sample size adjustment

Interim comparative data will be most securely protected from inadvertent or inappropriate access by the Sponsor. Sponsor will remain blinded to all information except the DMC recommendations.

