**Statistical Considerations**

The study is designed as an adaptive trial and will allow for stopping early for efficacy, futility and potential adjustment in sample size based on the results of a planned interim analysis. Approximately 573 subjects are planned to be randomized 1:1:1 per treatment group (191 per treatment group) assuming approximately 10% will drop out prior to 48 weeks. This sample size would provide approximately 90% power to detect a 2.5-point difference between active treatment group and placebo with respect to change from baseline ADAS-Cog 11 score at Week 48, assuming a standard deviation of 7.1 at a two-sided significance level of 0.05 using a two-sided test. The ADCS-ADL was added as a co-primary outcome, with assumptions of a 3.9-point difference between the active treatment group compared to placebo with respect to change from baseline on ADCS-ADL, assuming a standard deviation of 10.5, providing approximately 95% power on this outcome measure, with approximately 90% power for the overall co-primary outcomes, depending on their correlation.

An unblinded interim analysis will be conducted by a firewalled independent statistician (all clinical trial personnel will remain blinded) when approximately 100 subjects per arm have completed the Week 24 visit. Overwhelming efficacy, futility and sample size adjustment will be evaluated. The Lan-DeMets spending function will be used to determine the test boundaries. If the interim analysis is conducted when approximately 300 subjects have completed the Week 24 visit, then a significance level of 0.005 will be used for the interim analysis and a

significance level of approximately 0.0456 will be used for the final analysis.  
Further details are provided in the statistical analysis plan (SAP).

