### **11.3.2.3 Multiplicity**

To control for type I error, for the interim and final analysis will be adjusted using the Lan-DeMets spending function. If the study does not stop at the interim analysis (i.e., 24 weeks ADAS-Cog and CDR-SB as co-primary endpoints) for overwhelming efficacy or futility, the study will retain its original design and the final analysis will be based on 48 weeks of treatment with ADAS-Cog and ADCS-ADL as co-primary endpoints. Because of the changes in co-primary endpoint at 48 weeks (i.e., CDR-SB 24-week replaced by ADCS-ADL at 48-week and ADAS-Cog 24-week replaced by ADAS-Cog 48-week), the Lan-DeMets correction for sequential analysis will be further adjusted as described in [Chen et al., \(2014\)](#). This adjustment will account for the correlation between the outcomes and time points. The boundaries will be calculated to account for the change in timing of evaluation and endpoint and the more conservative boundary will be used for final analysis at 48-week.

At both the interim analysis at 24 weeks and final analysis at 48 weeks, to adjust for comparison between placebo and each of the two doses, Benjamini-Hochberg multiplicity adjustment procedure ([Benjamini and Hochberg, 1995](#) and [Benjamini and Yekutieli, 2001](#)) will be used. Both treatment comparisons, 40 mg (low dose) and 80 mg COR388 HCl (high dose) to placebo are considered of equal interest.

Treatment comparisons of 40 mg and 80 mg COR388 HCl to placebo for the secondary endpoints at 24-week or 48-week will be performed only if both co-

primary endpoints compared to placebo are statistically significant at the level of approximately 0.005 or 0.0456 for the interim analysis and final analysis, respectively. Otherwise, secondary endpoints will be presented using descriptive statistics.

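### Is it a fault that the interim futility rule stops a dose only when it looks worse than placebo?

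*Protocol*

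**What the plan says.** The synopsis (Statistical Considerations) says the design "will allow for stopping early for efficacy, futility and potential adjustment in sample size", and of the interim it says "Overwhelming efficacy, futility and sample size adjustment will be evaluated". Section 11.3.2.3 also treats futility as a way to stop: if the trial does not stop "for overwhelming efficacy or futility, the study will retain its original design".

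The only criterion is the second of four possible DMC recommendations in section 11.3.5. It begins "Stop either or both arms (stopping both arms would mean stopping the study) early for futility defined as" and requires p < 0.05 on ADAS-Cog 11 or CDR-SB "in favor of placebo over active dose(s), and the other endpoint for the same dose is directionally favoring placebo". Both endpoints are taken at Week 24, with about 100 subjects per arm.

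Two other statements bear on how the rule is run:

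- **Sidedness.** Section 11.3.5 does not state it. The sample size text is two-sided: "assuming a standard deviation of 7.1 at a two-sided significance level of 0.05 using a two-sided test". Section 11.2 says the same.
- **Adjustment across doses.** Section 11.3.2.3 applies Benjamini-Hochberg at the interim as well as the final analysis ("to adjust for comparison between placebo and each of the two doses, Benjamini-Hochberg multiplicity adjustment procedure"). Section 11.3.5 mentions it for the efficacy recommendation and not for the futility one.

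**The concern.** A futility stop is normally understood as a way to end an arm that is unlikely to show benefit. An arm with no observed benefit does not meet this rule. One endpoint must be significantly worse than placebo and the other numerically worse. In behaviour this is a harm rule, and a sponsor, DMC or ethics committee reading only the synopsis could believe the interim guards against continuing a useless drug when it hardly does.

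There is also a point of execution. A DMC statistician who follows section 11.3.2.3 would adjust across the two doses before applying the 0.05 threshold, while one who follows section 11.3.5 would not. On some data they would recommend differently for an arm.

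**Working it through.** **1. The plan's own figure.** The protocol gives no operating characteristic for this rule. The nearest stated figure is about 90% power on ADAS-Cog 11 (section 11.2: 172 per arm, difference 2.5, SD 7.1, two-sided 0.05). The standard error is 7.1 × √(2/172) = 0.766, and 2.5/0.766 = 3.27. Power is Φ(3.27 − 1.96) = 0.904, so the figure reproduces under the two-sided convention. I use that convention for the rule too, which puts 0.025 in the direction of placebo.

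**2. One arm, inert drug.** Let Z1 and Z2 be the two endpoint statistics, positive when placebo is better, with correlation ρ. Then

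P(arm meets rule) = 2·P(Z1 > 1.96, Z2 > 0) − P(Z1 > 1.96, Z2 > 1.96).

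At ρ = 0 this is 2 × 0.025 × 0.5 − 0.025² = 0.0244. Sample size cancels out under the null. The protocol gives no value of ρ for ADAS-Cog 11 and CDR-SB at Week 24, so a range is shown.

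**3. Two arms.** With 1:1:1 allocation and a shared placebo arm, the two dose comparisons correlate 0.5. The unadjusted two-arm columns come from 4 million simulated trials per ρ. The Benjamini-Hochberg column (across the two doses, within endpoint) comes from 2 million.

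| ρ | given arm | at least one arm | both arms (study stops) | given arm, Benjamini-Hochberg |
|---|---|---|---|---|
| 0 | 2.4% | 4.5% | 0.4% | 1.4% |
| 0.3 | 3.6% | 6.5% | 0.7% | 2.2% |
| 0.5 | 4.1% | 7.3% | 0.8% | 2.5% |
| 0.6 | 4.2% | 7.5% | 0.9% | not run |
| 0.7 | 4.1% | 7.3% | 0.9% | 2.4% |
| 0.9 | 3.5% | 6.3% | 0.7% | 2.1% |

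An inert arm therefore continues in about 96–98% of trials and the study in more than 99%.

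**4. What triggers the rule.** With 100 per arm, the observed ADAS-Cog 11 worsening that gives p < 0.05 is 1.96 × SD × √(2/100). That is 1.97 points at SD 7.1 (the Week 48 planning value) and 1.39 points at an assumed Week 24 SD of 5. Against the 2.5-point design difference these are 1.97/2.5 = 79% and 1.39/2.5 = 55%, in the wrong direction.

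**5. Response to real worsening.** Suppose both doses are truly worse by 1.0 point, with the same standardised worsening on CDR-SB, ρ of 0.3–0.7 and SD 5–7.1. A given arm then stops in 24–44% of trials. At 0.5 point worse it stops in 11–17%. The rule reacts to harm and barely reacts to absence of effect.

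**6. Does the text contradict itself?** Section 11.3.5 names the term and defines it in the same sentence. The synopsis and section 11.3.2.3 use the term without any threshold, conditional power or other rule. Nothing in them conflicts with the definition.

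**7. Does the final inference change?** Stopping an arm because placebo looks better can only remove a chance to claim efficacy. It cannot add a false claim, so the type I error is not raised.

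**The case for a change.** The strongest case for acting is that a stopping rule for an unblinded committee should be named for what it does and be executable in only one way. The synopsis is what many people read, and there the bare word suggests a protection that is absent in more than 99% of trials of an inert drug, counted by whether the study continues. The fix would be cheap: a different label, a sentence saying there is no stop for lack of benefit, and a sentence on the adjustment.

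Two parts of this stand. The word is used in an unusual sense, and the scope of Benjamini-Hochberg is open, with per-arm null rates of 1.4–2.5% if it applies and 2.4–4.2% if it does not.

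The rest is weaker. Those who act on the rule read section 11.3.5, where it is explicit. Doubt about sidedness has little basis, because no part of the protocol mentions a one-sided test. Adding a direction to the p-value follows the same form as the efficacy recommendation beside it. On the adjustment, section 11.3.2.3 introduces its corrections as type I error control, which a stop in favour of placebo does not threaten. The more specific section 11.3.5 leaves the adjustment off this item. Section 11.3.5 also refers the interim analyses to the SAP, and section 12.6 gives the decision rules to the DMC Charter, so the detail has a natural home outside the protocol.

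**Conclusion.** The observation is correct, but no change to the plan follows. The rule called futility is a rule for worsening: under an inert drug it stops a given arm in 2.4–4.2% of trials, at least one arm in about 4.5–7.5% and the study in 0.4–0.9%. These figures assume normal test statistics, two-sided p, equal arms and an endpoint correlation between 0 and 0.9. The conclusion is the same across that range and with or without Benjamini-Hochberg.

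Having no stop for lack of benefit at Week 24 is a fair trade-off. Section 4.1.1 chose 48 weeks so that a difference would have time to appear, and a stricter look at half that time could end an arm too early. Because the criterion is fully defined, relabelling would alter no recommendation, sample size, error rate or final result. The remaining ambiguity about the adjustment is small, concerns a committee recommendation and not a claim of efficacy, and can be settled in the SAP or DMC Charter before unblinding.

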### 11.3.6 Pharmacokinetic Analysis

Plasma levels of COR388 will be determined from blood samples collected at Visit 2, Visit 3, Visit 7, Visit 9, and Visit 10 (or Early Termination).

Descriptive statistics (sample size, mean, SD, minimum, median, and maximum) will be calculated for all results. Geometric mean and geometric coefficient of variation (CV)% will also be calculated for PK parameters.

## 12 STUDY MANAGEMENT

### 12.1 Regulations and Guidelines

The study will be performed in accordance with this protocol, United States IND regulations (21 Code of Federal Regulations [CFR] 312) or local national laws (as applicable), ICH guidelines for Good Clinical Practice, and the most recent

guidelines of the Declaration of Helsinki. These guidelines are on file at the Sponsor and/or CRO.

## **12.2 Institutional Review Board/Independent Ethics Committee**

Conduct of the study must be approved by an appropriately constituted IRB or IEC. Approval is required for the study protocol, investigational drug brochure, protocol amendments, ICFs, subject information sheets, and advertising materials. No investigational product will be shipped to a site until written IRB/IEC authorization has been received by the Sponsor or its representative.

## **12.3 Discontinuation of the Study by the Sponsor**

The Sponsor reserves the right to discontinue the study at this site or at multiple sites for safety or administrative reasons at any time. In particular, a site that does not recruit at a reasonable rate may be discontinued. Should the study be terminated and/or the site closed for whatever reason, all documentation and investigational product pertaining to the study must be returned to the Sponsor or its representative.

## **12.4 Study Documentation**

By signing a copy of Form FDA 1572 or other country-specific regulatory forms, the Principal Investigator acknowledges that he/she has received a copy of the IB on COR388 HCI and assures the Sponsor that he/she will comply with the protocol and the provisions stated in Form FDA 1572 and other country-specific forms. No changes in this protocol can be made without the Sponsor's written approval.

## **12.5 Study Monitoring and Auditing**

This study will be monitored for quality assurance at all stages of its development by the clinical research personnel employed by the Sponsor or its representative. Monitoring will include remote (virtual) data reviews, personal visits, and telephone communication to assure that the investigation is conducted according to the protocol, standard operating procedures, Guidelines of Good Clinical Practice, and applicable regulatory requirements. Quality control procedures will be applied to each stage of data handling to ensure that all data are reliable and have been processed correctly. On-site and remote review of eCRFs will include a review of forms for completeness and clarity, and consistency with source documents available for each subject. Note that a variety of original documents, data, and records will be considered as source documents in this trial. Procedures for handling source documents remotely will be described in the Clinical Monitoring Plan. The eCRF itself is not to be used as a source document under any circumstances.

Medical advisors and Clinical Research Associates (CRAs) or assistants may request to witness subject evaluations occurring as part of this protocol. The Investigator and appropriate personnel will be periodically requested to attend

meetings/workshops organized by the Sponsor to assure acceptable protocol execution. The study may be subject to audit by the Sponsor or by regulatory authorities. If such an audit occurs, the Investigator must agree to allow access to required subject records. By signing this protocol, the Investigator grants permission to personnel from the Sponsor, its representatives, and appropriate regulatory authorities, for remote and on-site monitoring of all appropriate study documentation, as well as on-site review of the procedures employed in eCRF generation, where clinically appropriate.

## **12.6 Data Monitoring Committee**

An independent Data Monitoring Committee (DMC) will be established to review accumulating study data to monitor the safety of subjects enrolled in COR388-010 on an ongoing basis and review the interim analysis (see [Section 11.3.5](#)). All members will be independent of the study (e.g., not a participating site employee, Cortexyme employee, etc.).

The DMC will review data on a regular basis. After reviewing the safety data, the DMC may make a recommendation to continue the study with or without modification or terminate the study. The DMC Charter defines all DMC responsibilities, functions, membership, meeting structure, communications, DMC SAP, and rules for decision making.

## **12.7 Retention of Records**

The Investigator must arrange for retention of study records at the site. The nature of the records and the duration of the retention period must meet the requirements of the relevant regulatory authority. In addition, because this is an international study, the retention period must meet the requirements of the most stringent authority. The Investigator should take measures to prevent accidental or premature destruction of these documents.

## **12.8 Use of Study Findings**

By signing the study protocol, the Investigator agrees to the use of results of the study for the purposes of national and international registration. If necessary, the authorities will be notified of the Investigator's name, address, qualifications, and extent of involvement. Reports covering clinical and biometric aspects of the study will be prepared by the Sponsor or its representative.

## **12.9 Publications**

As a multicenter trial, the Sponsor intends to publish clinical data from all centers participating in the investigation. A publication committee selected by the Sponsor will submit draft manuscripts to all participating investigators for their comments. In conformity with the Uniform Requirements for Manuscripts Submitted to Biomedical Journals published by the International Committee of Medical Journal Editors (see

discussion in [Kassirer & Angell, 1991](#)), investigators whose contribution consists solely in the collection of data will not be named individually as authors. Rather, those investigators will receive a collective authorship as the “COR388 Study Group” and will be identified in a note.

Individual investigators and/or their associates subsequently may publish additional findings of this study in scientific journals or present them at scientific meetings, provided that the Sponsor is given ample opportunity to review any proposed abstract, manuscript, or slide presentation before its submission. This review is required to ensure that the Sponsor is aware of all written and oral presentations of the data and does not imply any editorial review or restriction of the contents of the presentation or use.

### **12.10 Subject Privacy**

To maintain subject confidentiality, all eCRFs, study reports, and communications relating to the study will identify subjects by initials and assigned subject numbers. As required by federal regulations, the Investigator will allow Cortexyme and/or the CRO CRA access to all pertinent medical records in order to allow for the verification of data gathered in the eCRFs and for the review of the data collection process. The FDA (or other regulatory authority) may also request access to all study records, including source documentation for inspection.

As applicable, in accordance with Health Insurance Portability and Accountability Act (HIPAA) and associated privacy regulations, a subject authorization to use personally identifiable health information may be required from each subject prior to research activities. This authorization document must clearly specify what parties will have access to a subject’s personal health information, for what purpose, and for how long.

### **12.11 Amendments to the Protocol**

Any amendments to the study protocol will be communicated to the investigators by the CRO or the Sponsor. All protocol amendments will undergo the same review and approval process as the original protocol. A protocol amendment may be implemented after it has been approved by the IRB/IEC, and, where appropriate, competent regulatory authority approval prior to implementation, unless immediate implementation of the change is necessary for subject safety. In this case, the situation must be documented and reported to the IRB within 5 working days and in the countries outside of the United States according to the national regulation.

Any departures from protocol must be fully documented in the source documentation and in a protocol deviation log.

### **12.12 Case Report Form Completion**

Electronic CRFs (eCRFs) will be employed for this study. Completed eCRFs for this study will be forwarded to the Sponsor or its representative, where editing and

construction of a quality-assured database will occur. Data will be quality checked, double-entered, and electronically verified before entry into the database. Queries will be issued for any inconsistencies, omissions, and discrepancies and will be resolved by the appropriate parties. The statistical analysis of these data will be performed by the Sponsor or its representative. All AEs will be coded using the latest version of the Medical Dictionary for Regulatory Activities (MedDRA). Concomitant medications will be coded using the latest version of the World Health Organization Drug Dictionary. Data management details will be outlined in a separate data management plan.

